## **5.2.5 Assessment of other safety parameters**

### **5.2.5.1 Vital signs**

[figure not shown]
Systolic and diastolic blood pressures (BP) as well as pulse rate (PR) will be measured by a blood pressure monitor (Dinamap, GE Medical Systems, Freiburg, Germany) at the times indicated in the [Flow Chart](#), after subjects have rested for at least 5 min in a supine position and after ECG recording was taken. All recordings should be made using the same type of blood pressure recording instrument on the same arm if possible.

### **5.2.5.2 Medical examinations**

At the screening visit, the medical examination will include documentation of subject information, informed consent, demographics including height and body weight, smoking and alcohol history, relevant medical history and concomitant therapy, review of inclusion and exclusion criteria, review of vital signs (BP, PR), 12-lead ECG, laboratory tests, and a physical examination. At the end of trial examination, it will include review of vital signs, 12-lead ECG, laboratory tests, and a physical examination with determination of weight.

5.2.5.3 Ophthalmological examination

A slit lamp examination (Carl Zeiss Jena RSL 110) will be conducted by an ophthalmologist at screening, Day 15, Day 29 and EOT to exclude findings suspicious for signs of cataract.

## 5.4 APPROPRIATENESS OF MEASUREMENTS

All measurements performed during this trial are standard measurements and will be performed in order to monitor subjects' safety and to determine pharmacokinetic and pharmacodynamic parameters in an appropriate way. The scheduled measurements will allow monitoring of changes in vital signs, standard laboratory values, and ECG parameters that might occur as a result of administration of trial medication. The safety assessments are standard, are accepted for evaluation of safety and tolerability of an orally administered drug, and are widely used in clinical trials. The pharmacokinetic parameters and measurements outlined in [Section 5.5](#) are generally used assessments of drug exposure. The biomarker measurements outlined in [Section 5.6](#) are of exploratory nature only.

## 5.5 DRUG CONCENTRATION MEASUREMENTS AND PHARMACOKINETICS

Date and clock time of drug administration and exact time points of blood sampling will be documented in the CRFs by the medical personnel. The actual sampling times will be used for determination of pharmacokinetic parameters.

PK sampling times and periods may be adapted during the trial based on information obtained during trial conduct (e.g. preliminary PK data) including addition of samples and visits as long as the total blood volume taken per subject does not exceed 510 mL. Such changes would be implemented via non-substantial CTP Amendments.

### 5.5.1 Pharmacokinetic endpoints

The following pharmacokinetic parameters will be determined if feasible:

[figure not shown]
#### 5.5.1.1 Secondary endpoints

[figure not shown]
After the first dose (Day 1):

- $AUC_{0-24}$  (area under the concentration-time curve of the analyte in plasma over the time interval from 0 to 24 hours after administration of the first dose)
- $C_{max}$  (maximum measured concentration of the analyte in plasma after administration of the first dose)

After the last dose (Day 28):

- $AUC_{0-24,28}$  (area under the concentration-time curve of the analyte in plasma over the time interval from 0 to 24 hours after administration of the 28th dose)
- $C_{max,28}$  (maximum measured concentration of the analyte in plasma following administration of the 28th dose)

## 5.5.2 Methods of sample collection

### 5.5.2.1 Plasma sampling for pharmacokinetic analysis

For quantification of BI 1467335 plasma concentrations, approx. 2.7 mL of blood will be taken from an antecubital or forearm vein into a K3-EDTA (tripotassium ethylenediaminetetraacetic acid)-anticoagulant blood drawing tube at the times indicated in the [Flow Chart](#). Blood will be withdrawn by means of either an indwelling venous catheter or by venipuncture with a metal needle.

30 µL phenelzine solution (approx. 50 mM/L) will be added to all blood samples before withdrawal. All blood samples will be centrifuged using a cooled centrifuge at about 2000 x g to 4000 x g and at a temperature of 4 - 8°C for at least 10 minutes (intermittent storage on ice). The obtained K3-EDTA plasma will be split into two cryotubes (e.g. Nunc tubes) which will be frozen immediately and not later than 60 min after blood sampling with interim storage on ice. One of the aliquots should contain at least 0.7 mL plasma. The second aliquot containing the remaining plasma will be used as analytical back-up sample. Until transfer on dry ice to the analytical laboratory, the plasma samples will be stored frozen and in upright position at about -20°C or below at the clinical site and at the analytical laboratory until analysis.

After completion of the trial the plasma samples may be used for further methodological investigations, e.g. for stability testing, assessment of metabolites. However, only data related to the analyte and/or its metabolite(s) will be generated by these additional investigations. The study samples will be discarded after completion of the additional investigations but not later than 5 years upon the final study report has been signed.

### 5.5.2.2 Plasma sampling for drug metabolism analysis

Additional K3-EDTA plasma samples for the identification of drug metabolites will be investigated in all dose groups. The blood samples will be drawn in parallel to the PK

samples on Day 28 to 29 (see [Flow Chart](#)). At each of these time points, 2.7 ml blood will be needed for metabolite analysis. The blood samples will be centrifuged using a cooled centrifuge at about 2000 x g to 4000 x g and at a temperature of 4 - 8°C for at least 10 minutes (intermittent storage on ice). The obtained K3-EDTA plasma (approximately 1 mL) will be transferred into a single polypropylene tube. Samples will be stored at about -70°C or below until transfer to the metabolism laboratory.

At a minimum, the sample tube labels should list the following information: BI trial number, subject number, visit, planned sampling time and 'MetID'. Further information such as matrix and analyte may also be provided.

Metabolite analysis will be performed under non-GxP conditions in the laboratory of

Boehringer Ingelheim Pharma GmbH & Co. KG  
Drug Metabolism and Pharmacokinetics  
[name]  
[name]

Only data related to the parent compound and its metabolites will be acquired. Evaluation of the drug metabolism will be reported separately but not included in the CTR of this trial. The study samples will be discarded after completion of the experiments but not later than 3 years after the final study report has been signed.

#### 5.5.2.3 Urine sampling for pharmacokinetic analysis

A blank urine sample will be collected before administration of trial medication (within 2 h before drug dosing) and two 0.5 mL aliquots will be retained to check for analytical interference by concomitant or rescue medication.

All urine voided during the sampling intervals indicated in the [Flow Chart](#) will be collected in 2 L polyethylene (PE) containers and stored at room temperature. Subjects will be told to empty their bladders at the end of each sampling interval.

The urine weight/volume (weight will be set equal to volume, i.e. 1 kg = 1 L, without correction for specific gravity of urine) for each collection interval will be documented and two 2 mL aliquots (e.g. Nunc tubes) will be stored for bioanalytical measurement. The weight of the empty container will be determined and the weight of the container at the end of each sampling interval will be determined.

Until transfer to the analytical laboratory, the urine samples will be stored at about -20°C or below at the clinical site and stored at the analytical laboratory at -20°C or below until analysis. The back-up aliquots will be transferred to the analytical laboratory after the bioanalyst has acknowledged safe arrival of the first aliquot.

After completion of the trial the urine samples may be used for further methodological investigations, e.g. for stability testing, assessment of metabolites. However, only data related to the analyte and/or its metabolite(s) will be generated by these additional investigations. The study samples will be discarded after completion of the additional investigations but not later than 5 years upon the final study report has been signed.

#### 5.5.2.4 Additional blood sample for stability-testing

In order to assess the stability of the analyte in whole blood, one additional blood sample each on days 1, 14 and 28 will be taken from all subjects of dose group 10 mg and 15 mg.

Approximately 3.6 mL blood will be taken from an antecubital or forearm vein using three 1.2 mL K3 EDTA-blood drawing tubes at the time indicated in the [Flow Chart](#) (immediately after the drawing of a regular blood PK sample, which is to say that no additional venous puncture will be necessary).

To the first two 1.2 mL K3 EDTA-blood drawing tubes 10µL phenelzine solution (approx. 50 mM/L) will be added before taken from all subjects of dose group 1 and 2 at the time indicated in the [Flow Chart](#).

Approx. 0.5 mL of plasma will be generated out of each blood sample:

- Sample handling for stability samples of dose group 2, procedures will be provided in a separate lab manual. Blood sample one ('stability reference') will be centrifuged within 10 min after collection. Centrifugation will last for about 10 min (at about 2000 g to 4000 g and 4 to 8 °C), plasma will be separated and transferred into a freezer.
- Blood sample two and three ('stability test') will be stored for about 4 h at room temperature and ambient light conditions (documentation of storage time necessary) and will then be centrifuged and stored according to the first sample. To the plasma sample from blood sample three 5µL phenelzine solution (approx. 50 mM/L) will be added before freezing.

At a minimum, the aliquots should be labelled with the following information: BI trial number, administered drug, subject number, planned sampling time, 'stability reference' or 'stability test'.

Until transfer to the analytical laboratory, all aliquots will be stored at about -20 °C or below at the clinical site. All aliquots will be provided to the responsible bioanalyst together with the information about sample handling (i.e. storage time of 'test sample' at room temperature). After receipt, the aliquots will be stored at the bioanalytical laboratory at about -20°C or below until analysis.

The results of the analysis of these samples will not be reported within this clinical trial but will be used for bioanalytical assay validation and therefore included in the corresponding method validation report. The remaining sample volume will be discarded upon completion of the method validation report at the latest.

### 5.5.3 Analytical determinations

#### 5.5.3.1 Analytical determination of BI 1467335 plasma concentration

BI 1467335 concentrations in plasma will be determined by a validated LC-MS/MS (liquid chromatography tandem mass spectrometry) assay.

The analysis will be performed at:

Boehringer Ingelheim Pharma GmbH & Co. KG  
Drug Metabolism and Pharmacokinetics  
[name]  
[name]

[figure not shown]
As described in [Section 4.1.5](#), the bioanalyst will be unblinded during sample analysis.

[figure not shown]
[figure not shown]
[figure not shown]
5.5.3.2 Analytical determination of analyte urine concentration

[figure not shown]
BI 1467335 concentrations in urine will be determined by a validated LC-MS/MS assay

The analysis will be performed at:

Boehringer Ingelheim Pharma GmbH & Co. KG  
Drug Metabolism and Pharmacokinetics  
[name]  
[name]

## 6. INVESTIGATIONAL PLAN

### 6.1 VISIT SCHEDULE

Exact times of measurements outside the permitted time windows will be documented. The acceptable time windows for screening and end of trial examination are given in the [Flow Chart](#).

Study measurements and assessments scheduled to occur 'before' trial medication administration on Day 1, Day 14, and Day 28 are to be performed and completed within a 2 h-period prior to the trial drug administration (including blank values for PK and biomarkers collected predose on Day 1).

The acceptable deviation from the scheduled time for vital signs, ECG and laboratory tests will be  $\pm 30$  min for the first 4 h after trial drug administration and  $\pm 30$  min thereafter when not already stated otherwise in the flowchart.

If scheduled in the [Flow Chart](#) at the same time as a meal, blood sampling, vital signs and 12-lead ECG recordings have to be done first. Furthermore, if several measurements including venipuncture are scheduled for the same time, venipuncture should be the last of the measurements due to its inconvenience to the subject and possible influence on physiological parameters.

For planned individual plasma concentration sampling times and urine collection intervals refer to the [Flow Chart](#). While these nominal times should be adhered to as closely as possible, the actual sampling times will be recorded and used for determination of pharmacokinetic parameter.

If a subject misses an appointment, it will be rescheduled if possible. The relevance of measurements outside the permitted time windows will be assessed no later than at the Blinded Report Planning Meeting.

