## 5.2.4 Electrocardiogram

### 5.2.4.1 12-lead resting ECG

Twelve-lead resting ECGs (I, II, III, aVR, aVL, aVF, V1 - V6) will be recorded using a computerised electrocardiograph (CardioSoft EKG System, GE Medical Systems, Freiburg, Germany) at the time points given in the [Flow Chart](#). Electrode placement will be performed according to the method of Wilson, and modified Goldberger and Einthoven (Mason-Likar). The same electrode positions on a specific subject should be used for all ECG recordings throughout the study.

Triple ECGs (recorded within 180 sec) will be recorded on all time points on Day 1, Day 2, Day 14, Day 15, Day 21, Day 28 and Day 29. On all other visits/time points single ECGs will be obtained. ECGs may be repeated for quality reasons (like alternating current artefacts, muscle movements, electrode dislocation). For time points with triple ECGs, all three single ECGs will be repeated.

In order to achieve a stable heart rate at rest and to assure high quality recordings at comparable resting phases, all ECGs will be recorded for 10-sec duration after the subjects have rested for at least 5 min in a supine position. The site personnel will be instructed to assure a relaxed and quiet environment so that all subjects are at complete rest during the recordings. ECG assessment will always precede all other study procedures of the same time point (except blood drawing from an intravenous cannula which is already in place) to avoid impact of sampling on the ECG quality.

All locally printed ECGs will be evaluated by the investigator or a designee. Additional (unscheduled) ECGs may be collected by the investigator for safety reasons. These ECGs are assigned to the prior scheduled time point. Unscheduled ECGs will not be included into the statistical analysis of interval lengths.

For the inclusion or exclusion (see [Section 3.3](#)) of a subject and for the assessment of cardiac safety during the study, the QT and QTcB values generated by the ECG machines or their manual corrections by the investigators will be used. In doubtful cases, ECGs may be sent upfront for centralized evaluation (see below). In this case, these centrally measured results would overrule any other results obtained.

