A centralised evaluation of all 12-lead ECGs recordings (see [Section 5.2.4](#)) will be the basis for the derivation of further ECG parameters based on the ECG variables QT, HR, QTcF, QTcB, PR, QRS, and RR. The baseline value of an ECG variable is defined as the mean of the triple ECG measurements prior to drug administration. It is planned to evaluate the difference to placebo of change from baseline for QTcF, QT and HR over time via a repeated measurements model as well as the exposure response relationship of change from baseline for QTcF, QT and HR. More details on this and further analysis as well as the derivation of the quantitative and qualitative ECG endpoints are given in the TSAP.

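### Section 6.1 sets the same ±30 min before and after 4 h, so the windows of all adjacent ECGs from 0:15 to 2:00 overlap

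*Protocol*

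**What the plan says.** Section 6.1 gives one tolerance rule, which covers vital signs, ECGs and laboratory tests alike. The permitted departure from schedule is ± "30$ min for the first 4 h after trial drug administration and $\pm 30$ min thereafter", unless the flow chart states something else. The flow chart footnotes set no window for post-dose ECGs. Footnotes 2 and 14 concern procedures and samples before dosing, and footnote 8 only says which ECGs are triplicate.

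On recording of times, Section 6.1 says: "Exact times of measurements outside the permitted time windows will be documented". For PK samples it goes further: "the actual sampling times will be recorded and used for determination of pharmacokinetic parameter".

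Section 5.2.4.1 controls the spread within a replicate set: "Triple ECGs (recorded within 180 sec) will be recorded on all time points on Day 1" and on certain later days. It puts the ECG before other procedures of the same time point, "except blood drawing from an intravenous cannula which is already in place".

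Section 7.3.3 plans to "evaluate the difference to placebo of change from baseline for QTcF, QT and HR over time via a repeated measurements model", and also to study the "exposure response relationship of change from baseline for QTcF, QT and HR".

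**The concern.** A sentence that divides the day at 4 h and then gives the same figure for both parts does nothing with the division. Either one of the two figures is wrong or the split is redundant, and the protocol does not show which.

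The early figure is also wider than the spacing it governs. The flow chart places ECGs 15 to 30 min apart in the first 2 h, and the amendment log records that the 15-minute ECG was added on purpose. Such a dense series is useful only if each recording is close to its planned time. Under the stated rule an ECG may lie up to 30 min away without being a deviation, and Section 6.1 does not ask for its exact time. In the time-course model, recordings assigned to neighbouring time points could then mix, and an early effect would be expected to blur. In the exposure-response analysis, an ECG could be separated from the concentration it is matched with. The order rule in Section 5.2.4.1 does not limit that separation, because it exempts blood drawn from a cannula already in place.

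**Working it through.** **Inputs.** Half-width of the window: 30 min (Section 6.1), so each window is 60 min wide. ECG times on Days 1 and 14 (flow chart): 0:15, 0:30, 0:45, 1:00, 1:30, 2:00, then 4:00, 8:00 and 12:00 after dosing.

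**Formula.** Window = planned time ± 30 min. Overlap of adjacent windows = 60 min − gap between planned times; a negative result means clear time between them.

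| ECG | Window | Gap to next (min) | Overlap with next (min) |
|---|---|---|---|
| 0:15 | −0:15 to 0:45 | 15 | 60 − 15 = 45 |
| 0:30 | 0:00 to 1:00 | 15 | 45 |
| 0:45 | 0:15 to 1:15 | 15 | 45 |
| 1:00 | 0:30 to 1:30 | 30 | 60 − 30 = 30 |
| 1:30 | 1:00 to 2:00 | 30 | 30 |
| 2:00 | 1:30 to 2:30 | 120 | none (60 clear) |
| 4:00 | 3:30 to 4:30 | 240 | none (180 clear) |

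All five adjacent pairs from 0:15 to 2:00 overlap. Four non-adjacent pairs overlap as well: 0:15 with 0:45, 0:15 with 1:00, 0:30 with 1:00, and 0:45 with 1:30.

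**Span shared by the four first-hour windows.** Latest opening: 1:00 − 0:30 = 0:30. Earliest closing: 0:15 + 0:30 = 0:45. Four separate time points could thus be recorded within the same 15 min with no deviation.

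**Day 28.** The flow chart as available shows no ECG mark at 15 min, but the table may be damaged there. From 0:30 to 2:00 the four adjacent pairs overlap by 45, 45, 30 and 30 min.

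**Vital signs.** These are scheduled at 0:30, 0:45, 1:00 and 2:00. The two adjacent pairs within 0:30 to 1:00 overlap by 45 min each, and 0:30 with 1:00 overlaps by 30 min. The 1:00 and 2:00 windows only touch, at 1:30.

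**Width at which overlap ends.** The half-width must not exceed half the gap: 15 / 2 = 7.5 min for 0:15 to 1:00, and 30 / 2 = 15 min for 1:00 to 2:00. As an illustration, ±5 min for 0:15 to 1:00 and ±10 min from 1:30 to 4:00 leaves clear gaps of 5, 5, 5, 15, 10 and 100 min, and the first window opens at 0:10, after dosing.

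**The case against.** The strongest reply is that a tolerance is a limit, not a plan. Nothing suggests that a site would record four triplicates in one quarter of an hour. ECGs are computerised and digitally recorded, and Section 4.1.5.1 blinds the readers to recording date and time, which implies that both are captured. Section 7.3.3 leaves the detail of the ECG models to the TSAP, which is not available here and may use actual times. The window opening before dosing at 0:15 is a strained reading, since Section 6.1 treats pre-dose measurements separately.

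Much of this stands. The calculation shows what the rule permits, not that recordings will drift. Time stamps probably exist, so the gap is in the instruction and perhaps not in the data. The pre-dose opening is a drafting loophole that concerns a single ECG. What does not follow is that the rule is adequate. Actual times can correctly label a displaced recording, but they cannot put it back where the schedule wanted it. No other provision sets a tighter post-dose ECG window.

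It is also fair to say that a blanket change would tighten vital signs and the isolated 1-h ECGs on other days, where no post-dose windows overlap. For vital signs this is reasonable, because their 0:30 to 1:00 windows overlap too. For the isolated ECGs it is a matter for the sponsor.

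**Conclusion.** The concern holds. The 4-h split in Section 6.1 has no effect as written, and ±30 min is two to four times the largest half-width that would keep the early ECG windows apart (30 / 15 = 2; 30 / 7.5 = 4). On Days 1 and 14 all five adjacent pairs from 0:15 to 2:00 overlap. From 2:00 onward the problem ends.

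The conclusion rests on the flow chart times as extracted and on the absence of a narrower window elsewhere in the protocol. The size of any blurring cannot be derived from the document: it depends on how far recordings actually move and on how the TSAP handles actual times.

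Severity is minor. Section 7.2 makes the analyses exploratory. The primary endpoint, subjects with drug-related adverse events, and the individual QT stopping rule in Section 3.3.4.1 do not depend on the planned-time label of an ECG.

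**What to change.** Replace the first ±30 min in Section 6.1 with a window below half the scheduled gap: under 7.5 min for 0:15 to 1:00 and under 15 min up to 2:00. The ±5 and ±10 min in the illustration meet this limit, but the sponsor should set the values. Keep ±30 min after 4 h. State whether the tighter window applies on all days or only on those with dense ECG sampling. Add that post-dose ECGs are taken after dosing and that the actual time of every ECG is documented, as is already required for PK samples.

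The cost is one or two amended sentences and no extra ECGs. More time deviations will be logged, and the intensive days become tighter, because each recording needs at least 5 min of supine rest and a triplicate, with blood draws and often vital signs due at the same point. Documenting actual times should cost little with digital recordings.

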### 6.2 DETAILS OF TRIAL PROCEDURES AT SELECTED VISITS

#### 6.2.1 Screening

After having been informed about the trial, all subjects will give their written informed consent in accordance with GCP and local legislation prior to enrolment in the study.

For information regarding laboratory tests (including drug and virus screening), ECG, vital signs, and physical examination, refer to [Sections 5.2.3](#) to [5.2.5](#).

Before first dosing on day 1 pharmacogenomic genotyping will be performed in all subjects (for details see [Section 5.3](#)).

